11.2.1.1 Consultation with Medical Monitor and local hepatologist

Potential drug-induced liver injury events require notification of the Medical Monitor within 24 hours (eg, by laboratory alert), and the subject must be discussed with the Medical Monitor as soon as possible. If required, the subject must also be discussed with the local hepatologist. The local hepatologist is the expert usually consulted by the treating physician for assessment and management of potential hepatic disease. This would usually be a hepatologist, but may be a gastroenterologist. If determined necessary, this discussion should be followed by a full hepatology assessment (see Section 11.2.1.3) and SAE report (if applicable).

11.2.1.2 Immediate action: determination of IMP discontinuation

All PDILI events require immediate action, testing, and monitoring.

The immediate action is dependent on the laboratory values and symptoms of hepatitis or hypersensitivity and ranges from continuation of IMP (followed by immediate investigation) to immediate and permanent discontinuation (see Section 6.3.1 and Table 11-2 for details).

When IMP is discontinued, all concomitant medications and herbal supplements that are not medically necessary should also be discontinued. The investigator should also consider dose reduction for medically necessary concomitant medication and consider changing any medically required concomitant medication known to be hepatotoxic to a suitable alternative.

11.2.1.3 Testing: identification/exclusion of alternative etiology

The measurements and additional information required for the assessment of PDILI events when there is a reasonable possibility that they may have been caused by the IMP are detailed in Table 11-3 (laboratory measurements) and Table 11-4 (additional information). Results of the laboratory measurements and information collected are to be submitted to the sponsor on the corresponding CRF. If the medical history of the subject indicates a requirement for other assessments not included below, these additional assessments should be completed and submitted, as applicable.

All blood samples should be stored, if possible. If tests are done locally for more rapid results, a concurrent sample must also be sent to the central laboratory.

The following measurements are to be assessed:

Table 11–3: PDILI laboratory measurements

Virology-related	Hepatitis A IgM antibody
	HBsAg
	Hepatitis E IgA antibody
	HBcAb-IgM
	Hepatitis C RNA
	Cytomegalovirus IgM antibody
	Epstein-Barr viral capsid antigen IgM antibody (if unavailable, obtain heterophile antibody or monospot testing)
Immunology	Anti-nuclear antibody (qualitative and quantitative)
	Anti-smooth muscle antibody (qualitative and quantitative)
	Type 1 anti-liver kidney microsomal antibodies (qualitative and quantitative)
Hematology	Eosinophil count
Urinalysis	Toxicology screen
Chemistry	Amylase
	If total bilirubin $\geq 1.5 \times$ ULN, obtain fractionated bilirubin to obtain % direct bilirubin
	Serum CPK and LDH to evaluate possible muscle injury causing transaminase elevation
Additional	Prothrombin time/INR ^a
	PK sample

ALT=alanine aminotransferase; CPK=creatine phosphokinase; HBcAb-IgM=hepatitis B core antibody-IgM; HBsAg=hepatitis B surface antigen; IgA=immunoglobulin A; IgM=immunoglobulin M; INR=international normalized ratio; LDH=lactate dehydrogenase; PDILI=potential drug-induced liver injury; PK=pharmacokinetic; RNA=ribonucleic acid; ULN=upper limit of normal

^a Measured only for subjects with ALT $>8 \times$ ULN, elevations in total bilirubin, and symptoms of hepatitis or hypersensitivity. Hepatitis symptoms include fatigue, nausea, vomiting, and right upper quadrant pain or tenderness; hypersensitivity symptoms include eosinophilia ($>5\%$), rash, and fever (without clear alternative cause).

The following additional information is to be collected:

Table 11–4: PDILI information to be collected

New or updated information
Concomitant prescription and over-the-counter medications (eg, acetaminophen, herbal remedies, vitamins); dosages and dates should be included.
Pertinent medical history, including the following: 
History of liver disease (eg, autoimmune hepatitis, nonalcoholic steatohepatitis or other “fatty liver disease”)Adverse reactions to drugsAllergiesRelevant family history or inheritable disorders (eg, Gilbert’s syndrome, alpha-1 antitrypsin deficiency)Recent travelProgression of malignancy involving the liver (Note: Metastatic disease to the liver, by itself, should not be used as an explanation for significant AST and/or ALT elevations.)
The appearance or worsening of clinical symptoms of hepatitis or hypersensitivity (eg, fatigue, nausea, vomiting, right upper quadrant pain or tenderness, decreased appetite, abdominal pain, jaundice, fever, or rash)
Recent clinically significant hypotension or hypoxemia with compromised cardiopulmonary function
Alcohol and illicit drug use
Results of liver imaging or liver biopsy, if done
Results of any specialist or hepatology consult, if done
Any postmortem/pathology reports

ALT=alanine aminotransferase; AST=aspartate aminotransferase; PDILI=potential drug-induced liver injury

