11.2.1 Evaluation of PDILI

The PDILI IMP discontinuation criteria for this study are provided in Section 6.3.1, with the accompanying required follow-up investigation and monitoring detailed below. All PDILI events must be reported as an AE and reported to the study site and sponsor within 24 hours of learning of their occurrence. Any PDILI event that meets the criterion for potential Hy's Law must be reported as an AE of special interest (see Section 11.1.1.3), and, if applicable, also reported as an SAE (see Section 11.1.1.2).

Evaluation of PDILI consists of the diagnostic testing and continued monitoring included in Table 11–2 (specific tests dependent on laboratory results and corresponding symptoms) and consultation with a local hepatologist (if applicable; discussed in Section 11.2.1.1). The local hepatologist is the expert usually consulted by the treating physician for assessment and management of potential hepatic disease. This would usually be a hepatologist, but may be a gastroenterologist. Additional investigation and monitoring may be required and adapted based on the diagnosis after the cause of the liver injury/abnormality is confirmed (details in Section 11.2.1.4).

The results of all monitoring, including laboratory testing and other testing, should be made available to the study site and sponsor.

All initial tests resulting in abnormal hepatic laboratory values need to be repeated, but appropriate medical action must not be delayed waiting for the repeat result.

If tests are done locally for more rapid results, a concurrent sample should also be sent to the central laboratory whenever possible. Medical care decisions are to be made initially using the most rapidly available results and a conservative approach must be taken if the results from the 2 laboratory tests are significantly different. Data from the local and central laboratory are to be recorded on the applicable eCRF pages.

When IMP is discontinued, all concomitant medications and herbal supplements that are not medically necessary should also be discontinued. In these cases, the investigator should also consider dose reduction for medically necessary concomitant medication and consider changing any medically required concomitant medication known to be hepatotoxic to a suitable alternative.

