When IMP is stopped due to PDILI (as described in Section 6.3.1), IMP must be permanently discontinued unless a subsequent alternative diagnosis fully explains the hepatic findings. If a subsequent alternative diagnosis fully explains the hepatic findings, and the requirements provided in Section 11.2.1.3 are met, rechallenge with IMP may be appropriate.

Rechallenge with a substance potentially causing drug-induced liver injury is dangerous, may be fatal, and must not occur.

The table below summarizes the approach to investigate PDILI.

This document cannot be used to support any marketing authorization application and any extensions or variations thereof.

Table 11–2: Required investigations and follow up for PDILI

Laboratory value		Symptoms ^a of hepatitis or hypersensitivity	Immediate		Follow up	
ALT or AST	Total bilirubin		Consultation requirements	Actions	Testing	Evaluation
≥3xULN	≥2xULN ^b	NA	Hepatology consult. ^c Medical Monitor must be notified within 24 hours (eg, by laboratory alert) and subject discussed with Medical Monitor ASAP.	Immediate, permanent IMP discontinuation.	Essential: Must have repeat liver chemistry values and additional testing completed ASAP (see Section 11.2.1.3); recommended to occur at the site with HCP.	Monitoring of liver chemistry values at least twice per week until values normalize, stabilize, or return to within baseline values. ^d
≥8xULN	NA	NA		Immediate, temporary or permanent, IMP discontinuation.		
≥3xULN	NA	Yes				
≥3xULN (and ≥2x baseline) and <5xULN	<2xULN	No	Discussion with Medical Monitor required if the criterion that allows for IMP continuation is met.	Further investigation – immediate IMP discontinuation not required (see Section 11.2.1.2).	Not required unless otherwise medically indicated (at discretion of investigator).	

Table 11–2: Required investigations and follow up for PDILI

Laboratory value		Symptoms ^a of hepatitis or hypersensitivity	Immediate		Follow up	
ALT or AST	Total bilirubin		Consultation requirements	Actions	Testing	Evaluation

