≥5xULN (and ≥2x baseline) and <8xULN	<2xULN	No	Hepatology consult if there is no evidence of resolution (see Follow up requirements). ^c Discussion with Medical Monitor required.	IMP discontinuation required if any of the following occur: Subject cannot comply with monitoring schedule. Liver chemistry values continue to increase during 2 week monitoring period. Liver chemistry values remain ≥5xULN (and ≥2x baseline) after 2 week monitoring period.	Essential: Every attempt must be made to have repeat liver chemistry values and additional testing completed within 48 hours at the site with HCP (see Section 11.2.1.3).	Monitoring of liver chemistry values at least twice per week for 2 weeks. ^d Immediate IMP discontinuation required if liver chemistry values continue to increase. After 2 weeks of monitoring liver chemistry values: Discontinue IMP if levels remain ≥5xULN (and ≥2x baseline); monitor until values normalize, stabilize, or return to within baseline values. ^d Continue IMP if levels are no longer ≥5xULN (and ≥2x baseline); continue to monitor at least twice per week until values normalize, stabilize, or return to within baseline values. ^d

ALP=alkaline phosphatase; ALT=alanine aminotransferase; ASAP=as soon as possible; AST=aspartate aminotransferase; HCP=healthcare practitioner;

IMP=investigational medicinal product; NA=not applicable; PDILI=potential drug-induced liver injury; ULN=upper limit of normal

^a Hepatitis symptoms include fatigue, nausea, vomiting, and right upper quadrant pain or tenderness; hypersensitivity symptoms include eosinophilia (>5%), rash, and fever (without clear alternative cause).

^b If the subject also has ≥2xULN ALP, the possibility of an indication of biliary obstruction should be discussed with the Medical Monitor.

^c Details provided in Section 11.2.1.1. The local hepatologist is the expert usually consulted by the treating physician for assessment and management of potential hepatic disease. This would usually be a hepatologist, but may be a gastroenterologist.

^d Unless an alternative monitoring schedule is agreed by the investigator and UCB responsible physician. Determination of stabilization is at the discretion of the investigator in consultation with the hepatologist (as applicable) and UCB responsible physician, as needed.

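### As worded, the PT/INR footnote to Table 11-3 does not require INR for a child with ALT or AST ≥3xULN and bilirubin ≥2xULN unless ALT also exceeds 8xULN and symptoms are present; it also leaves out AST

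*Protocol*

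**What the plan says.** Protocol Section 11.2.1.3 presents Table 11-3 as the set of laboratory measurements required when a PDILI event may reasonably have been caused by the study drug. PT/INR is one of them, subject to footnote a. The footnote begins "Measured only for subjects with ALT", sets the ALT level at above 8xULN, and continues "elevations in total bilirubin, and symptoms of hepatitis or hypersensitivity". SAP Section 12.3.4 carries the same footnote. PT/INR is not in the routine panel (Table 11-1), and neither document requires it anywhere else.

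Protocol Section 11.2.1 says that the work-up follows Table 11-2, with the "specific tests dependent on laboratory results and corresponding symptoms". Row 1 of that table covers ALT or AST ≥3xULN with total bilirubin ≥2xULN and marks symptoms as not applicable. It calls for immediate, permanent discontinuation, as does Section 6.3.1. Its testing cell is labelled essential, points to Section 11.2.1.3, and reads "Must have repeat liver chemistry values and additional testing completed ASAP". It also requires a hepatology consult and says "Medical Monitor must be notified within 24 hours". Section 11.1.1.3 makes the same pattern potential Hy's Law, reportable as an adverse event of special interest, if ALP is below 2xULN and there is no alternative explanation.

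**The concern.** The word *only* makes the footnote a restriction, and *and* makes it cumulative. The result does not fit the table it serves. Row 1 of Table 11-2 ignores symptoms and starts at 3xULN, whereas the footnote asks for symptoms and more than 8xULN. Table 11-2 uses ALT or AST throughout, whereas the footnote names ALT alone.

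At stake is whether a test of liver function is a required part of the work-up for one of the most serious liver patterns the protocol defines. The symptom condition is also a weak gate at 1 month to <4 years. Fatigue, nausea and right upper quadrant pain largely depend on the patient's report, although vomiting, tenderness, fever, rash and eosinophilia can still be observed.

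**Working it through.** No figure in the plan is involved, so the check is one of logic: footnote a against the rows of Table 11-2.

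**Inputs.** The five rows of Table 11-2 (Section 11.2.1), assuming that the testing cell of row 1 spans rows 2 and 3:

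| Row | ALT or AST | Total bilirubin | Symptoms | Section 11.2.1.3 testing |
|---|---|---|---|---|
| 1 | ≥3xULN | ≥2xULN | not applicable | essential |
| 2 | ≥8xULN | not applicable | not applicable | essential |
| 3 | ≥3xULN | not applicable | yes | essential |
| 4 | ≥3 to <5xULN (and ≥2x baseline) | <2xULN | no | not required unless medically indicated |
| 5 | ≥5 to <8xULN (and ≥2x baseline) | <2xULN | no | essential |

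Testing is essential in 4 of the 5 rows. In row 5 the cell reads "Every attempt must be made to have repeat liver chemistry values and additional testing completed within 48 hours".

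**Rules compared.** The footnote gives no threshold for raised bilirubin, so I take it as above ULN.

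- *And* reading: ALT >8xULN, and bilirubin raised, and symptoms.
- *Or* reading: ALT >8xULN, or bilirubin raised, or symptoms.
- Proposed wording: ALT or AST ≥8xULN, or bilirubin raised, or symptoms.

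**Are a row's own criteria enough to require INR?**

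| Row | *And* | *Or* | Proposed |
|---|---|---|---|
| 1 | no: also needs ALT >8xULN and symptoms | yes | yes |
| 2 | no: also needs bilirubin and symptoms | only if ALT itself is >8xULN | yes |
| 3 | no: also needs ALT >8xULN and bilirubin | yes | yes |
| 5 | never: ALT is <8xULN and there are no symptoms | only if bilirubin is >ULN and <2xULN | only if bilirubin is >ULN and <2xULN |

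Rows whose criteria are enough without further conditions: 0 of 4 (*and*), 2 of 4 (*or*), 3 of 4 (proposed). These count table rows, not children.

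**Illustrative cases** (multiples of ULN; AST matters only where stated):

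| Case | *And* | *Or* | Proposed |
|---|---|---|---|
| ALT 6, bilirubin 3, no symptoms | no | yes | yes |
| ALT 4, bilirubin 2.5, symptoms | no | yes | yes |
| ALT 10, bilirubin 2.5, no symptoms | no | yes | yes |
| AST 10, ALT 4, bilirubin 2.5, symptoms | no | yes | yes |
| ALT 10, bilirubin 2.5, symptoms | yes | yes | yes |
| AST 10, ALT 4, bilirubin normal, no symptoms | no | no | yes |
| ALT 6, bilirubin normal, no symptoms | no | no | no |
| ALT 4, bilirubin 1.8, no symptoms | no | yes | yes |

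The first five cases all fall in row 1, and only the fifth has a required INR under the literal wording. The sixth falls in row 2 and shows that the missing AST matters even on the *or* reading. The last falls in row 4 if ALT is also ≥2x baseline, so it arises only if the testing is done at all.

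**Nothing is lost.** ALT >8xULN implies ALT or AST ≥8xULN, and the other two conditions are unchanged. Every child covered by either reading of the present footnote is therefore covered by the proposed wording.

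**The case against.** The strongest reply is that *and* need not be cumulative. A phrase of the form 'subjects with A, B and C' can list three groups. The three elements resemble the triggers in rows 1 to 3 of Table 11-2 (bilirubin, 8xULN, symptoms), and Section 11.2.1 ties the tests to that table. This stands as to probable intent. It does not settle the matter, because the text never says so, sites could apply it differently, and the list reading still omits AST.

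The second reply is that the child is under specialist care. Row 1 requires a hepatology consult and prompt Medical Monitor contact. Section 11.2.1.3 also provides for further tests ("If the medical history of the subject indicates a requirement for other assessments not included below"), and Table 11-4 collects "Results of any specialist or hepatology consult, if done", so an INR ordered by the consultant would be captured. This is a real backstop, but none of these provisions requires INR. The further-tests clause depends on medical history and concerns tests outside the table, whereas INR is in the table with a restriction.

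The third reply is that no protocol decision uses INR. This is correct. Discontinuation and potential Hy's Law are defined without it.

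A reader might infer more than the documents support on two points. One is that INR is forbidden or would not be done in these children. The footnote limits the required study panel, and nothing prevents a clinically ordered INR. The other is that leaving out row 5 with normal bilirubin and no symptoms is part of the same error. Neither reading of the footnote covers that child, so including it would be a new testing policy. Section 6.3.1 does not settle the point either: it stops drug permanently at ≥5xULN, but row 5 of Table 11-2 lets drug continue under monitoring.

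**Conclusion.** The point holds as a defect of wording with a limited safety consequence. Followed literally, footnote a leaves a row 1 child without a required INR unless ALT is also above 8xULN and symptoms are present, although that row makes the testing essential and stops drug permanently.

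It would be too strong to conclude that the sponsor meant the three conditions to be cumulative, or that the trial's safety decisions or results are compromised. The effect is confined to the PDILI work-up and the listing of PDILI laboratory results in SAP Section 10.3. No stopping rule, efficacy analysis or SAP summary depends on INR.

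The number of children affected cannot be estimated, because the documents give no PDILI frequency. The row counts rest on reading the row 1 testing cell as covering rows 2 and 3, and raised bilirubin as above ULN. The main conclusion about row 1 needs neither assumption.

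**What to change.** Reword footnote a of Table 11-3 to: *Measured for subjects with PDILI who have any of the following: ALT or AST ≥8xULN, or elevation in total bilirubin, or symptoms of hepatitis or hypersensitivity.* The present definitions of the symptoms can stay. This removes the ambiguity, adds AST and matches the ≥8xULN threshold of Table 11-2.

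Make the same change in SAP Section 12.3.4. That table does not govern what sites measure, and it differs from Table 11-3 in other entries (the hepatitis A and E antibody classes, and a serum pregnancy test), so it needs a full check against the protocol.

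Extending INR to the 5 to <8xULN row with normal bilirubin and no symptoms is optional and a clinical choice.

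The cost is one footnote, its SAP copy and a note to sites. The downside is an occasional additional coagulation sample in a child who may weigh as little as 3.0 kg at entry (inclusion criterion 5).

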11.2.1.4 Follow-up evaluation

Potential drug-induced liver injury events require follow-up monitoring as described in Section 11.2.1. Monitoring should continue until liver chemistry values normalize, stabilize, or return to baseline. Determination of stabilization is at the discretion of the investigator in consultation with the hepatologist (as applicable) and UCB responsible physician, as needed.

11.3 Other safety measurements

11.3.1 Physical examination

A physical examination will be performed by medically qualified clinicians licensed to perform the examination at Visit 1. Height will be measured according to schedule of study assessments.

11.3.2 Neurological examination

A neurological examination will be performed at Visit 1. The neurological examination should be conducted by a medically qualified clinician with documented training in the conduct of

neurological examinations. The investigator or subinvestigator is responsible for confirming the diagnosis of partial seizures or other epilepsy syndrome.

11.3.3 Vital signs and body weight

Blood pressure (systolic and diastolic), pulse rate, and body temperature will be measured at all visits. Body weight will be determined according to the schedule of study assessments.

11.3.4 12-lead ECG

Standard 12-lead ECGs will be performed according to the schedule of study assessments.

11.3.5 Assessment of suicidality

Suicidality will be assessed by trained study personnel using the C-SSRS (Columbia University Medical Center, 2008). For subjects ≥ 6 years of age, this scale will be used to assess suicidal ideation and behavior that may occur during the study. The C-SSRS will be completed according to the tabular schedule of study procedures.

The C-SSRS is not validated and will not be used for subjects < 6 years of age. Subjects should be monitored for any changes in mood, ideas, or behavior for warning signs of depression. The investigator should be aware of common warning signs that might be a signal for risk of depression. For common signs and symptoms of depression in children younger than 6 years old, reference should be made to the current version of the Diagnostic and Statistical Manual of Mental Disorders. Parents and caregivers should also be advised accordingly and effort should be made at clinic visits to specifically assess potential depression.

12 STUDY MANAGEMENT AND ADMINISTRATION

12.1 Adherence to protocol

The investigator should not deviate from the protocol. However, the investigator should take any measure necessary in deviation from or not defined by the protocol in order to protect clinical study subjects from any immediate hazard to their health and safety. In this case, this action should be taken immediately, without prior notification of the regulatory authority, IRB/IEC, or sponsor.

After implementation of such measure, the investigator must notify the CPM of the sponsor within 24 hours and follow any local regulatory requirements.

12.2 Monitoring

Monitoring of the study will be delegated by UCB to a CRO. The CRO will monitor the study to meet the CRO's monitoring Standard Operating Procedures (SOPs), ICH GCP guideline, and applicable regulatory requirements, and to ensure that study initiation, conduct, and closure are adequate. Monitoring of the study may be delegated by UCB to a CRO or a contract monitor.

The investigator and his/her staff are expected to cooperate with UCB (or designee) and to be available during the monitoring visits to answer questions sufficiently and to provide any missing information. The investigator(s)/institution(s) will permit direct access to source data/documents for study-related monitoring, audits, IRB/IEC review, and regulatory inspection(s).

The investigator will allow UCB (or designee) to periodically review all eCRFs and corresponding source documents (eg, hospital and laboratory records for each study participant). Monitoring visits will provide UCB (or designee) with the opportunity to evaluate the progress of the study, verify the accuracy and completeness of eCRFs, ensure that all protocol requirements, applicable authorities regulations, and investigator's obligations are being fulfilled, and resolve any inconsistencies in the study records.

